1. Participants randomised to ApBM will consume significantly fewer standard drinks per week than participants in the minimal condition, as measured using self-report 4 weeks after commencing training (post-intervention; primary endpoint), and at 1-month and 3-month follow-ups (secondary endpoints).

Secondary outcomes:

2. Participants randomised to ApBM will show significantly larger declines, compared to those in the minimal condition, in past-week frequency of alcohol craving at post-intervention and follow-up assessments (relative to baseline craving frequency), as assessed by the frequency scale of the Craving Experience Questionnaire.
3. Participants randomised to ApBM will show significantly larger declines than those in the minimal condition in Severity of Dependence Scale scores at post-intervention and follow-up assessments (relative to baseline craving frequency).
4. Participants randomised to ApBM will show significantly larger declines than those in the minimal condition in Alcohol Use Disorders Identification Test (AUDIT) scores at the 3-month follow-up (relative to baseline scores).
5. Participants randomised to ApBM will have significantly fewer past-week heavy drinking days (HDDs, defined as ≥ 5 standard drinks in a day) than participants in the minimal

condition, as measured using self-report at post-intervention, 1-month, and 3-month follow-ups. Past-month HDDs will also be analysed post-intervention.

6. Participants randomised to ApBM will have significantly fewer past-month drinking days (i.e., days on which any alcohol is consumed) post-intervention and at 1- and 3-month follow-ups.
7. The proportion of participants reporting complete abstinence (i.e., 0 days on which any alcohol was consumed – both past week and past month will be analysed) will be significantly higher among participants in the ApBM than among those in the minimal condition at post-intervention and follow-up assessments.
8. Participants receiving ApBM will experience larger increases than those in the minimal condition in quality of life and health (assessed with 3 Australian Treatment Outcome Profile items) at post-intervention and follow-up assessments (relative to baseline).
9. There will be a significantly greater reduction in approach bias, as measured by the alcohol approach avoidance task, in participants assigned to the ApBM condition, compared to those in the minimal condition, between baseline and post-intervention.

Methods

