Design & Setting: We will conduct a double-blind, randomised, parallel-group controlled superiority trial with alcohol treatment outpatients at 6 AOD treatment services in Melbourne, Victoria. Participants will be randomised to one of 2 groups with a 1:1 allocation ratio. Both participants and researchers completing the follow-up interviews will be unaware (blinded) of the condition to which they have been randomly allocated.

Participants: We aim to recruit at least 300 participants receiving outpatient interventions for alcohol use disorder at the participating services. To be eligible, participants must, at the time of the screening interview:

- Be aged 18+
- Own an Android or iOS smartphone with an Australian mobile number
- Be currently accessing outpatient treatment for alcohol problems. (There is no requirement that alcohol be the *only* substance for which they are seeking treatment, and as such participants with multiple drugs of concern are eligible as long as alcohol is one of the drugs of concern for the current episode of treatment.)
- Have an Alcohol Use Disorders Identification Test (AUDIT) score of at least 8
- Not have been in residential rehabilitation within the past 4 weeks.
- Not have been in any form of inpatient treatment (e.g. hospital or residential withdrawal treatment) within the past week.
- Not entering inpatient/residential treatment within the next month.

The target sample size was determined based on practical considerations (likely recruitment rate, time available for recruitment), as there was little prior basis to estimate likely effect size of a personalised ApBM smartphone app in an outpatient client population. Nevertheless, a calculation conducted in GPower 3.1 suggested that the primary analysis (across 4 repeated measures) would have 90% power to detect a small time x group interaction effect size (partial eta squared of .01) with a sample of 178 participants (i.e., 59% retention at follow-ups). If recruitment proceeds quickly enough, we will aim to recruit more than 300 participants, to allow for increased statistical power in case attrition is larger than expected.

Measures:

Demographic information: Participants will be asked to enter their gender, the AOD service where they were recruited from, the date they began the current episode of treatment they are receiving from that service, and drugs of concern, in an online survey hosted on Qualtrics.

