variable size (ranging from 2-6). As such, randomisation will be stratified by site. The app developers (ANT Development Studios Ltd.) will provide the data scientist with two lists of app access codes which will direct participants to either the intervention or minimal version of AAT-App when they first download and open the app. Using these lists and the randomisation sequence, the data scientist will generate a separate spreadsheet of access codes for each site (based on the site-stratified randomisation sequence). Researchers will send these codes to participants as they are recruited from each respective site. Researchers involved in recruitment will only have access to a spreadsheet displaying a single list of codes to be sent to participants at each respective site, while the randomisation sequence will be stored in a password-protected file provided to the trial statistician and to one research officer who will remain unblinded to assist with coordinating qualitative interviews. Neither the randomisation file, nor its password will be provided to any other staff (including the principal investigator, [name], and research officer, [name]) involved in recruitment or in pursuing follow-ups or quantitative data management until all data analysis is complete.

Intervention: Prior to commencing the intervention, participants will be prompted to select 6 alcohol-related pictures that represent the drinks they most frequently consume. Participants can either select from their own photographs stored on their phone, take photographs of alcoholic beverages using the app, or select pictures from a library of 67 alcohol-related images chosen to represent a broad range of alcoholic beverages commonly consumed in Australia. Participants will then be prompted to select 6 pictures that “represent your goals and motivations”. Again, participants can either select their own photographs, take photographs, or select pictures from a library of 68 pictures representing a range of healthy activities or positive goals and sources of pleasure (including family or friends enjoying time together; financial success; employment; exercise, sports, and recreational activities; healthy foods; pets; travel and holidays) which do not contain any depictions of alcohol. If participants take/use their own photographs, they will be reminded to ensure that positive images do not contain depictions of alcohol.

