Audio-recorded qualitative interviews and verbal consent will be stored as .mp4 files on a secure Google drive hosted by Monash University, access to which will be restricted to project personnel (but which will not be made accessible to blinded quantitative data collectors until data collection is complete). The .mp4 files will be securely transferred to Pacific Transcription, a trusted transcription service provider that is frequently used by Monash University and Turning Point. To preserve participant anonymity the recording of verbal consent (where the participant states their full name and is also asked about their phone number) will be separated from the rest of the file and stored separately, while the main interview file will be labelled with a participant number (this number will be the same as the participant access code used to access the app, allowing baseline demographic data to be matched to qualitative interview data), not their name. Transcripts returned by Pacific Transcription will be stored as .docx files on the secure Google drive until data collection is complete. Once data collection is complete and blinding no longer required, these files will be stored in the project folder on the Turning Point Clinical Research Drive. They will be deleted from the Google Drive once analysis and publication is complete, and stored for at least 7 years following publication of the last paper arising from this study, or 7 years after the final report to the ethics committee, or 7 years after final reporting of outcomes on the clinical trials registry, whichever occurs latest.

Data Analysis

Statistical significance will be ascertained using $\alpha=.05$. Any participants who commenced at least 1 session of ApBM (if in the ApBM condition) or AAT (if in the minimal control condition) will be included in the analysis population.

Primary outcome: A linear mixed-effects model (LMM) will be used to compare change in mean standard drinks consumed per week between groups across 4 time points (baseline, post-intervention, 1-month follow-up, and 3-month follow-up). This model will test the main effects of time and group and (most crucially for determining efficacy) the group x time interaction. Planned follow-up comparisons between groups at post-intervention, 1-month follow-up, and 3-month

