follow-up time-points will be conducted using t-tests, with post-intervention being the primary endpoint. A secondary sensitivity analysis will be conducted excluding a participant's data from any time-point where they had been in residential/inpatient treatment in the past week (i.e., restricting analyses to time-points where a participant's opportunity to drink had not been limited by hospitalisation, rehabilitation, etc.). If a difference between groups is found post-intervention, a secondary LMM analysis of difference between groups in change in weekly standard drinks during the intervention period (i.e., 5 levels of time: Baseline, week 1, week 2, week 3, post-intervention) will be conducted to examine how quickly differences between groups emerge, with t-tests used to compare groups at week 1, 2, 3, and post-intervention time-points. This secondary analysis will be conducted excluding participants who had engaged in any residential/inpatient treatment within the intervention period.

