Secondary outcomes: Continuous outcome variables (CEQ, SDS, AUDIT, past-week HDDs, past-month drinking days, ATOP items, and approach bias) will be analysed in a similar manner to the primary analysis described above. In analyses of CEQ, SDS, past-week HDDs, past-month drinking days, and the 3 ATOP items, there will be 4 levels of time (baseline, post-intervention, 1-month, and 3-month follow-ups). Sensitivity analysis of past-week drinking days to control for the possible effect of past-week residential/inpatient treatment will be conducted as described for the primary outcome. Past-month drinking days will be expressed as a percentage of the total number of days on which a participant had the opportunity to drink (i.e., if a participant was in residential/inpatient treatment for 10 days at a certain time point, then for that time point, their past-month drinking days will be expressed as a proportion of the remaining 18 days on which they had the opportunity to drink), although data will be excluded at any time point where the participant did not have at least 14 days on which they had the opportunity to drink alcohol (i.e., if they were within residential/inpatient treatment on 15 or more days). For CEQ, secondary analyses will be conducted for each of its 3 subscales. Analyses of AUDIT scores will use 2 levels of time (baseline, 3-month follow-up). Approach bias analyses will also use 2 levels of time (baseline, post-intervention) and approach bias scores will be analysed separately for alcohol and positive images. As past-month HDDs can only be calculated at 1 time point (post-intervention), they will simply be compared between groups using a t-test post-intervention after converting scores to a proportion of days on which the participant had an opportunity to drink (as described for past-month drinking days). Proportions of groups reporting complete past-week and past-month abstinence will be compared between groups at post-intervention, 1-month follow-up, and 3-month follow-up using Pearson's chi-squared. uMARS "functionality", "aesthetics", and "subjective quality" scores, and participants' subjective ratings regarding AAT-App's effect on drinking and cravings will be explored within each group separately using descriptive data (e.g., mean, median, quartile cut-offs, percentages scoring above 3) to quantify typical ratings and proportions of participants providing favourable ratings. Where relevant, exploratory analyses will also compare mean scores of uMARS scales between groups using t-tests.

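### The 4-week difference is the primary endpoint, but the efficacy test and the power calculation concern a four-time-point interaction, and no rule says which result decides success

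*Combined protocol and SAP*

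**What the plan says.** **Primary endpoint.** Hypothesis 1 (Aims and Hypotheses) concerns weekly standard drinks and ranks the assessments: "post-intervention; primary endpoint), and at 1-month and 3-month follow-ups (secondary endpoints". Data Analysis, Primary outcome, repeats the ranking, with comparisons at the "follow-up time-points will be conducted using t-tests, with post-intervention being the primary endpoint".

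**Efficacy test.** The same paragraph fits a linear mixed model with four levels of time, baseline included. It tests main effects of time and group and "most crucially for determining efficacy) the group x time interaction". With two groups and four time points this test has 3 degrees of freedom.

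**Power.** The sample size paragraph under Methods, Participants, claims "90% power to detect a small time x group interaction effect size (partial eta squared of .01) with a sample of 178 participants". No power is given for the 4-week comparison.

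**The one conditional step.** "If a difference between groups is found post-intervention, a secondary LMM analysis of difference between groups" in the weekly data follows. The trigger is the 4-week difference, not the interaction.

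**Covariates and scope.** Neither the model nor the t-tests name baseline drinks as a covariate or a site term, although baseline drinks are collected and the Randomisation section states: "As such, randomisation will be stratified by site". The continuous secondary outcomes "will be analysed in a similar manner to the primary analysis described above".

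**The concern.** The two tests answer different questions. The interaction asks whether the group difference varies anywhere across baseline, 4 weeks, 1 month and 3 months, so it draws on visits the plan calls secondary. The t-test asks whether the groups differ at 4 weeks. Three decision rules fit the text, and each has a drawback:

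- **Interaction alone.** The trial could be called positive with no effect at the primary endpoint.
- **Either test.** Two 5% tests are used for one claim, which inflates type I error.
- **Interaction first, then the t-test.** Error is controlled, but power at the primary endpoint falls below the advertised 90%.

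With no rule in writing, the choice would be made after the results are seen, and with a real effect the two tests disagree often enough for that choice to matter.

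Separately, a t-test on raw 4-week values ignores baseline drinking and omits anyone missing at that visit.

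**Working it through.** **Inputs.** From the documents: alpha .05, 1:1 allocation, 178 evaluable (89 per arm), partial eta squared .01, four time points, at least 300 recruited, 59% retention (178/300 = .593). Assumed, because the documents give none of these: within-person correlation r (.3, .5 and .7 shown), normal data with equal correlation between all visits, two-sided t-tests, and the time pattern of the effect.

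**1. Reproducing the plan's figure.** f² = .01/.99 = .0101. Noncentrality = f² × N × 4/(1 − r). At r = .5 this is .0101 × 178 × 4/.5 = 14.38; on 3 and 528 df, power is 90.2%, matching the plan. At r = .3 and .7 it is 77.0% and 99.1%. So 178 is not wrong; it powers the interaction at r = .5.

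**2. The 4-week effect this implies.** For group differences (0, d, d, d), f² = ¼ × (3/16) × d². Hence d² = .0101/.0469 = .2155 and d = 0.464 SD. The 4-week t-test with 89 per arm then has 87% power; 90% would need 99 per arm. Other patterns with the same interaction size change this greatly. An effect growing linearly by visit gives d = 0.18 at 4 weeks and t-test power of 22%, while the interaction keeps 90%.

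**3. How the tests behave together.** Simulation with 89 per arm and complete data, 20,000 trials per alternative and 40,000 under the null. Entries are percentages at r = .3/.5/.7.

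| Scenario (SD at 4 weeks, 1 month, 3 months) | Interaction | 4-week t-test | Both | Exactly one | Baseline-adjusted 4-week contrast |
|---|---|---|---|---|---|
| Sustained (.464, .464, .464) | 77/90/99 | 87/87/87 | 68/79/86 | 28/19/14 | 90/94/99 |
| Fading (.464, .232, .116) | – | – | 59/72/84 | 31/22/14 | 90/94/99 |
| 3 months only (0, 0, .4) | 63/79/96 | about 5 | 4–5 | – | – |

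Under the null, at least one test is significant in 9.1–9.3% of trials and both in 0.6–1.0%.

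**4. Separating the gate from the covariate (sustained effect).** Gating costs .868 − .680, .871 − .790 and .868 − .862, or about 19, 8 and 1 points. Baseline adjustment adds .895 − .868, .944 − .871 and .991 − .868, or about 3, 7 and 12 points over the ungated t-test.

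**5. Larger sample.** With 150 per arm and no attrition, sustained effect: both tests 93/97/98%, adjusted contrast 99–100%.

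**6. Missing data.** 300 randomised, each follow-up seen with probability .593, independently and at random, d = 0.464:

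| 4-week contrast | Power, r = .3/.5/.7 |
|---|---|
| Raw t-test | 87/87/87% |
| Planned model, baseline as a time level | 89/92/94% |
| Model with baseline means constrained equal | 91/96/99% |

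The variance ratio of the raw t-test to the constrained model is 1.12/1.40/2.11, equivalent to 12/40/111% more participants. Against the planned model's own contrast the gain is 6/21/61%. If the same 59% attend every follow-up, the gain over the raw t-test is 10/33/96%.

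**7. Site.** Six sites, 8,000 simulated trials: power without and with a site term is .868 and .871 (ICC .02), .879 and .886 (.05), .880 and .896 (.10). Null rejection without site is .041–.049.

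**The case against.** The remark about efficacy ranks three terms inside one model; it does not expressly place the interaction above the 4-week comparison. Hypothesis 1 and the Data Analysis section both label 4 weeks primary, so the text leans that way. Calling the t-tests follow-up comparisons suggests an interaction-first sequence, under which error is controlled. Nothing in the plan permits success on either test, so the 9% is hypothetical. The plan's own figure corresponds to r = .5, where the disagreement is 19% and gated power 79%, and with 150 per arm the gating loss is small. Naming one test solves the decision problem with or without a covariate.

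Much of this stands. The 9% applies only if either test were allowed to count. The r = .5 column is the plan-consistent one. Baseline adjustment is an efficiency gain, separate from the decision rule, and site adds little. It does not remove the gap. An interaction-first sequence is never written as a rule, and the only conditional step bypasses the interaction by depending on the 4-week difference. If the sequence is intended, power at the primary endpoint is below the stated 90% at every correlation examined for 178 participants. A larger sample raises power but does not say which test decides.

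**Conclusion.** The concern holds and should be fixed. The named primary endpoint, the test singled out for efficacy and the powered test are not the same, and no decision rule connects them. At the plan's own setting (178 participants, r = .5, sustained 0.464 SD), the two tests disagree in about one trial in five. Power at 4 weeks is 87% for the t-test alone, 79% if both tests are required and 94% with baseline adjustment. An effect confined to 3 months would usually produce a significant interaction with nothing at the primary endpoint.

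These sizes rest on normal, equally correlated data, on assumed correlations and time patterns, and on an effect in SD units, because the documents give no SD or target difference in drinks for this trial. The absence of a rule depends on none of these assumptions.

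**What to change.** - Name one primary test: the 1-df group contrast at post-intervention from the mixed model, using all available data, with baseline weekly drinks as a covariate (or baseline means constrained equal) and site as a fixed effect. State that it alone decides success.
- Label the omnibus interaction and the 1- and 3-month contrasts supportive.
- Restate power for the 4-week contrast, giving the assumed correlation, retention and effect in SD units.
- Use model contrasts in place of t-tests for the listed continuous secondary outcomes. Past-month heavy drinking days, measured once, stay outside this. AUDIT and approach bias have two time levels, so their interaction already has 1 df and only the baseline adjustment is new.

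The cost is SAP wording, trivial programming and 5 df for six sites. No new data or participants are needed.

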Participants will be required to indicate that they have read and understood the information and consent to participate. This will result in the remaining baseline questionnaires being displayed including items assessing gender, which AOD treatment service the participant is attending, type(s) of treatment being accessed, drugs of concern, date of commencement of the current episode of treatment, treatment goal (abstinence or moderation), SDS, CEQ-F, and ATOP quality of life items. They will also be required to enter their smartphone number, and are encouraged to enter additional contact details (e.g., name, email, other phone numbers, and postal address) to assist with ensuring follow-ups are completed, although this is not required.

Completing the Qualtrics survey will result in an email being automatically sent to researchers, who will access the list of access codes, select the first unused code, and send the download link and access code to the participant via SMS. The researcher will record which access code was sent to which phone number. Once participants have downloaded the app, they will be prompted to enter the access code, thus resulting in either the ApBM or minimal version of the app being installed on their phone. Participants in the active condition will view a short introductory animation explaining how the ApBM intervention works, while participants in the minimal condition will be onboarded through written text that ensures blinding is maintained (see details provided above). Participants will then be required to complete the baseline alcohol consumption questions, before completing the pre-training VAS craving measure, the AAT, and the post-training VAS craving measure. Participants in the active condition will then proceed to the image selection feature, where they will be prompted to upload or select 6 alcohol-related images and 6 positive images to be used in the ApBM training task. These participants will then complete the pre-training VAS craving measure, their first session of the ApBM task, and the post-training VAS craving measure.

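### The primary-endpoint comparison is left as unspecified t-tests beside a mixed model with a free baseline difference, which gives up precision that baseline adjustment would recover at no cost

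*Combined protocol and SAP*

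**What the plan says.** Hypothesis 1 (Aims and Hypotheses) states the primary outcome as a difference in level of weekly drinks, "as measured using self-report 4 weeks after commencing training (post-intervention; primary endpoint".

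Data Analysis, Primary outcome, fits a linear mixed model to four time points, with baseline as one of them. Of that model it says: "This model will test the main effects of time and group and (most crucially for determining efficacy) the group x time interaction". The planned group comparisons at "follow-up time-points will be conducted using t-tests, with post-intervention being the primary endpoint". The type of t-test is not given. No baseline covariate, common baseline mean or site term is named, although Randomisation and blinding of allocation stratifies by site.

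Baseline drinking is collected in the app in both arms (Procedure): "Participants will then be required to complete the baseline alcohol consumption questions, before completing the pre-training VAS craving measure". The analysis population is limited to people who started at least one session, so under the planned sequence everyone analysed has a baseline value.

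Secondary outcomes: the continuous ones "will be analysed in a similar manner to the primary analysis described above".

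The power statement (Participants) covers only the time x group interaction: 90% power at partial eta squared .01 "with a sample of 178 participants (i.e., 59% retention at follow-ups". No power is stated for the post-intervention comparison.

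**The concern.** The comparison that carries the primary endpoint has three live readings:

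- a raw two-sample t-test on observed values;
- the group contrast at post-intervention from the mixed model;
- the contrast in change from baseline from the same model.

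A model contrast is the natural reading. The raw one is also possible, because the same section uses the same term for past-month heavy drinking days, which have a single time point and therefore no repeated-measures model.

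The readings differ in power, and which model contrast is better depends on a correlation the documents do not give. None uses the fact that randomised arms share one expected baseline mean. The result also has consequences within the plan: the week-by-week analysis is run only if a post-intervention difference is found. Sample size was set by practical considerations, with concern about attrition, so precision already in the data should be used.

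**Working it through.** **Inputs from the documents.** Recruitment target 300 at 1:1, so 150 per arm; 178 remaining, so 89 per arm (178/300 = 59%); alpha .05, taken as two-sided; four time points. The 59% is the retention at which 178 remain, not a forecast.

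**Assumptions.** r = .3, .5, .7; effect d = 0.40 SD; equal variances and equal correlations over time; baseline seen for all 150 per arm and all follow-ups for the same n per arm.

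**The plan's own figure.** Noncentrality = f² x N x 4/(1 - r), with f² = .01/.99 and df 3 and 3(N - 2). At N = 178 and r = .5 this is (.01/.99) x 178 x 4/.5 = 14.4, which gives 90.2% power. So N = 178 reproduces at r = .5; r = .3 would need 248 and r = .7 would need 108. The documents do not state r, and matching the plan's N is not evidence of its true value.

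**Variance of the post-intervention difference, relative to a raw t-test (n of 150 per arm observed).**

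- Group contrast, free baseline: (1 - r²) + r² x n/150
- Change contrast, free baseline: (1 - r²) + (1 - r)² x n/150
- Adjusted (common baseline mean): 1 - r²

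Generalised least squares on the four-time-point model gives the same values. The adjusted variance is lower by r² than the raw test, by r² x n/150 than the group contrast and by (1 - r)² x n/150 than the change contrast. All three are positive for r strictly between 0 and 1.

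Example, n = 89, r = .5: .75 + .25 x .593 = .898 for either model contrast, against .75.

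| n = 89 per arm | r = .3 | r = .5 | r = .7 |
|---|---|---|---|
| Relative variance: group contrast | .96 | .90 | .80 |
| Relative variance: change contrast | 1.20 | .90 | .56 |
| Relative variance: adjusted | .91 | .75 | .51 |
| Power, d = 0.40: raw t-test | 76% | 76% | 76% |
| Power: group contrast | 77% | 80% | 84% |
| Power: change contrast | 68% | 80% | 94% |
| Power: adjusted | 79% | 87% | 96% |

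Power is from the noncentral t with df 176. At r = .5 the gain over the model contrasts is worth 178 x (.898/.750 - 1) = 35 observed participants. With better retention at r = .5, power for the raw test, the model contrasts and the adjusted contrast is 87%, 89% and 95% at 120 per arm, and 93%, 93% and 98% at 150.

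**The group x time test.** For a constant difference d at all three follow-ups, the noncentrality with a common baseline is L = d² x (n/2) x 3/[(1 - r)(1 + 3r)]. With a free baseline it is L/[1 + (1 - r)² x (2/150) x L/d²]. At n = 89, r = .5, d = 0.40:

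- common: .16 x 44.5 x 3/1.25 = 17.1
- free: 17.1/(1 + .25 x .01333 x 106.8) = 12.6

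On 3 and 528 df, power is about 95% (common) and 86% (free).

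**Site.** If site explains an assumed 0 to 10% of the variance, leaving it out takes the type I error from 5.0% to 3.9%: slightly conservative, and minor.

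**The case against.** The case for leaving the plan alone has four parts.

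- *Validity.* Randomisation protects the planned comparison, and the mixed model already uses baseline in the group x time test. This stands. A reader might infer that the primary comparison is biased; the documents do not support that. Only the raw t-test reading could be biased, and only if drop-out depends on baseline drinking differently by arm, which no passage suggests. Either model contrast handles that pattern, so it is a reason to name the model contrast, not evidence for adjustment.
- *The interaction test uses baseline, so it escapes.* This does not stand. A free baseline difference costs that test power too, as calculated.
- *Unknown size.* This stands as a limit. At r = .3 the gain over the group contrast is about 2 points of power, and at r = .7 the gain over the change contrast is also about 2. The 35 participants belong to r = .5 alone. But the two unadjusted model contrasts change order between r = .3 and r = .7, so neither is a safe choice, while adjustment is at least as good throughout.
- *Onboarding comes before the baseline drinking report.* "Participants in the active condition will view a short introductory animation explaining how the ApBM intervention works", while control participants read text. If that shifted one arm's baseline report by s SD, the adjusted contrast would move by r x s (0.05 SD at s = 0.10, r = .5), the change contrast by s, and the unadjusted group contrast not at all. Nothing in the documents suggests such a shift. The caveat stands, and comparing baseline means is a weak check: their difference has SE √(2/150) = 0.115 SD, so a 0.10 SD shift would be detected about 14% of the time.

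**Conclusion.** The point holds as lost efficiency plus an open choice of test. On every reading of the t-tests, the primary-endpoint comparison is less precise than a baseline-adjusted contrast for r strictly between 0 and 1. With 89 of 150 per arm observed and d = 0.40, the adjusted contrast gains about 2 to 12 points of power over the group contrast and 2 to 12 over the change contrast for r from .3 to .7 (79 against 77 up to 96 against 84; 96 against 94 up to 79 against 68, from unrounded values). The joint group x time test loses about 9 points at r = .5 under a constant effect.

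These are ranges on assumed r and d, not estimates for this trial. They do not show that the trial is underpowered or that its result would be wrong. The direction does not depend on the assumed values; the size does.

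**What to change.** Before any unblinded analysis, including the student analyses that Interim analyses permits with the randomisation sequence, state the following.

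1. The group comparisons at post-intervention (primary), 1 month and 3 months are contrasts from one mixed model on all four time points, with a baseline mean common to both arms and site as a fixed effect.
2. The joint efficacy test is the 3-df test of the three post-baseline group differences in that model. If the free-baseline group x time test is kept instead, say that it comes from a separately fitted model. Entering baseline only as a covariate is not interchangeable here: baseline then stops being a time level, and group x time tests only whether the effect varies among the follow-ups.
3. The same approach applies to continuous secondary outcomes with a baseline value. It cannot apply to past-month heavy drinking days: "As past-month HDDs can only be calculated at 1 time point (post-intervention".
4. Baseline means are reported by arm, with the stated assumption that arm-specific onboarding does not change how baseline drinking is reported. AUDIT, SDS, CEQ-F and the ATOP items are collected before the access code is sent, so the assumption does not arise for them.
5. Neither the model nor the adjustment corrects for drop-out that depends on unobserved drinking.

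This is a free improvement: analysis-plan wording and minor programming, with no new data, participants or procedures.
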